## **8.7. Safety Monitoring**

Investigators are responsible for identifying, monitoring and reporting adverse events that occur throughout the study (from subject signing of informed consent through study exit). Any adverse event that is marked ‘ongoing’ at the exit visit should be followed-up as appropriate until the event is resolved or deemed chronic or stable by the Study Investigator.

### **8.7.1. Procedures for Collecting and Reporting Adverse Events**

Adverse events will be assessed, documented, and recorded in the eCRF throughout the study (ie, after informed consent has been obtained). At each visit, the investigator will begin by querying for adverse events by asking each subject a general, non-directed question such as “How have you been feeling since the last visit?” Directed questioning and examination will then be done as appropriate. All reported adverse events will be documented on the appropriate eCRF.

If, after obtaining the subject’s informed consent but prior to administration of study product/treatment, a medical condition is identified via a study entry protocol assessment or procedure (eg, screening ECG test) which, based on the Investigator’s judgment (and in consultation with the subject), is determined to be a pre-existing condition (ie, a condition existing prior to the time of the subject’s informed consent), it should be documented on the

appropriate eCRF. Otherwise, the condition should be reported as a pre-treatment adverse event.

All adverse events that are drug-related and unexpected (not listed as treatment-related in the current Investigator's Brochure) must be reported to the governing Institutional Review Board/Independent Ethics Committee (IRB/IEC) as required by the IRB/IEC, local regulations, and the governing health authorities.

#### **8.7.2. Severity**

A clinical determination will be made of the intensity of an AE. The severity assessment for an AE must be completed using the following definitions as guidelines:

Mild	Awareness of signs or symptoms, but easily tolerated
Moderate	Discomfort enough to cause interference with usual activity
Severe	Incapacitating with inability to work or do usual activity
Not Applicable	In some cases, an AE may be an 'all or nothing' finding that cannot be graded (eg, death)

#### **8.7.3. Relationship to Study Drug or Study Procedure**

A determination will be made of the relationship (if any) between an AE and the study drug or study procedure, as applicable. A causal relationship is present if a determination is made that there is a reasonable possibility that the AE may have been caused by the study drug or study procedure.

#### **8.7.4. Procedures for Reporting a Serious Adverse Event**

Any serious adverse event must be immediately reported but no later than 24 hours after learning of the serious adverse event. The first report should be submitted even if the available information is minimal. All subjects with a serious adverse event must be followed up and the outcomes reported. The investigator must supply Whitecap Biosciences and the IRB/IEC with any additional requested information (eg, autopsy reports, discharge summaries).

In the event of a serious adverse event, the investigator must:

1. Notify Whitecap Biosciences (or designee) immediately by email using the Serious Adverse Event Form; phone numbers and relevant Whitecap Biosciences (or designee) personnel contacts are on the front page of this protocol.

2. Obtain and maintain in his/her files all pertinent medical records, information, and medical judgments from colleagues who assisted in the treatment and follow-up of the subject.
3. Provide Whitecap Biosciences (or designee) with a complete, written description of the adverse event(s) on the Serious Adverse Event Form describing the event chronologically, including any treatment given (eg, medications administered, other treatments given) for the adverse event(s). Summarize relevant clinical information about the event: signs, symptoms, diagnosis, clinical course and relevant clinical laboratory tests, etc. Include any additional or alternative explanation(s) for the causality which includes a statement as to whether the event was or was not related to the use of the investigational drug.
4. Provide follow-up SAE reports to Whitecap Biosciences (or designee) as more information becomes available
5. Promptly inform the governing IRB/IEC of the serious adverse event as required by the IRB/IEC, local regulations, and the governing health authorities.

[REDACTED] additional details.

## **8.8. Procedures for Stopping Study Treatment**

Part 1- There are no specific procedures for stopping treatment.

Part 2 - When the study treatment is stopped for an individual subject prior to the protocol defined duration for study treatment administration, the Day 14/Exit (Hour 0) procedures, at a minimum should be performed. The reason that the study treatment is stopped should be documented on the appropriate eCRF.

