**Table 3 Part 2 - Schedule of Visits and Procedures: Day 1 to Day 14/Exit**

Outcome Assessment Visits (Visit window $\pm$ day)	Day 1 ( $\pm$ 0 day)		Days 4 ( $\pm$ 1 day) and 14 ( $\pm$ 2 days)				
Timepoint: All examinations for all visits and timepoints should be performed in the order listed below from top to [REDACTED] 12.2	H0	30 minutes post-1 st dose a	H2	H0	H2	H4	H8
Text or phone call from site reminding subject to dose approximately 12 hours prior to morning Hour 0 appointment				X			
Adverse Event Query	X			X			
Subject Comfort of Eye Drops Evaluation (administered by designated site personnel) (Day 1 and Day 14/Exit only)		X		X			
Concomitant Medications/Treatments	X			X			
Postural (Supine/Standing) Blood Pressure & Heart Rate	X		X	X	X		
Non-fasting Laboratory assessments (CBC with differential, Blood Chemistries, Urinalysis) (Day 14/Exit only, following final dose)						X	
Electrocardiogram (Day 14/Exit only)					X		
Urine Pregnancy Test (Day 14/Exit only, following final dose)						X	
Macroscopic (Gross) Hyperemia	X	X	X	X	X	X	X
[REDACTED]				X	X		
Visual Acuity b	X b			X b			
[REDACTED]				X			
Slit-Lamp Biomicroscopic Examination	X	X	X	X	X	X	X
Intraocular Pressure (IOP) c	X	X	X	X	X	X	X
Visual Field d (Day 14/Exit only)						X	
Fundus Exam (incl. C/D ratio) (post-pupil dilation) (Day 14/Exit only)							X
Confirm Inclusion / Exclusion criteria	X						
Randomize subject / Dispense study medication (for first dose) e	X						
Study medication administered by site personnel	X			X			
Collect subject EXIT status (Day 14/Exit only)							X

**NOTE:** C/D = cup/disc; H = hour (hour 0 = 07:00 to 09:00 hours)

**NOTE:** The night before postbaseline visits, evening dosing should occur approximately 12 hours (between 19:00 and 21:00 hours) prior to hour 0 of the subject's next morning's visit)

a Subject Comfort of Eye Drops Evaluation will be performed within 30 minutes post-morning dose.

b Manifest refraction performed at Baseline should be used at the days 1, 4 and 14 visits to obtain a correction for visual acuity evaluation. Manifest refraction(s) may be repeated, if in the opinion of the investigator, it is necessary.

c IOP should be measured before pupil dilation (as applicable) and at the same time ( $\pm$  15 minutes) each day as the time established at baseline (day -1, hour 0, between 07:00 and 09:00 hours).

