**Part 2 - Days 4 and 14/Exit (Hour 0) ( $\pm 10$  minutes)**

- Adverse event (AE) query
- Concomitant medications and treatments
- Postural (supine/standing) blood pressure and heart rate
- Macroscopic (gross) hyperemia evaluation
- 
- Visual acuity (VA): Manifest refraction performed at Baseline (Day -1) should be used for visual acuity evaluation. Manifest refraction(s) may be repeated, if in the opinion of the investigator, it is necessary.
- 
- Slit-lamp biomicroscopy
- IOP (GAT)
- Site to administer study medication at end of Hour 0 examination
- Site to collect study medication following final dose (Day 14/Exit only)

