**Part 2 - Day 14/Exit only, once final dose has been administered**

- Clinical laboratory evaluation (non-fasting)

- Urine pregnancy test (females of child-bearing potential only)

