**Part 2 - Days 4 and 14/Exit (Hours 4 and 8) ( $\pm 10$  minutes)**

- Macroscopic (gross) hyperemia evaluation
- Slit-lamp biomicroscopy
- IOP (GAT)
- Fundus exam (including cup/disc ratio, post-pupil dilation) (Day 14/Exit, Hour 8 only)

Following the completion of the Day 14/Exit examination, the subject will exit the study.

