## **8.9. Early Study Exit Procedures**

### **8.9.1. Subject Discontinuation/Withdrawal from the Study**

- A subject may withdraw from the study at any time at his/her own request, or may be withdrawn at any time at the discretion of the investigator for safety, behavioral, compliance, or administrative reasons;
- If the subject withdraws consent for disclosure of future information, the sponsor may retain and continue to use any data collected before such a withdrawal of consent;
- If a subject withdraws from the study, he/she may request destruction of any samples taken and not tested, and the investigator must document this in the site study records;
- A subject who is enrolled, but who had significant deviation from protocol-specified inclusion/exclusion criteria, may be discontinued from participation in the study;

- If a female becomes pregnant during the study, the investigator will notify Whitecap Biosciences immediately after the pregnancy is confirmed and the subject will stop taking study treatment. The subject will be discontinued from the study after appropriate safety follow-up. See Section 6.4.3 for Procedures for Pregnancy Follow-up and Reporting;
- Subjects who are exited before completing the study may be replaced.

See Schedule of Visits and Procedures for specific data to be collected at the time of study discontinuation and follow-up and for any further evaluations that need to be completed. If a subject is discontinued prior to completing the study, the procedures outlined for the Day 2/Exit visit (for Part 1) or the Day 14/Exit visit (Hour 0 timepoint at a minimum) for Part 2 should be performed at the last visit attended.

When a subject exits before completing the study, the reason for the early exit will be clearly documented on the appropriate eCRF.

If the subject exits before completing the study, any serious adverse events or treatment-related non-serious adverse events occurring within 14 days after the last dose of study treatment should be reported to the Site.

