**Table 8      Glossary of Definitions**

Term	Definition
End of Study	The date of the last visit of the last subject in the study
Subject Status	Subject status is defined below:
Study entry	A subject who has signed informed consent and has undergone at least 1 screening procedure and been entered into ITRS
In screening	A subject who has is undergoing the screening process and has not yet qualified for study enrollment.
Screen failure	Subject who has signed informed consent, has undergone at least 1 screening procedure, but fails to qualify for study at any time prior to and up until the completion of the Baseline visit.
Enrolled	A subject who qualifies for study based on Inclusion and exclusion criteria (Parts 1 and 2) (see Sections 4.1 and 4.2) AND is randomized (assigned a randomization number (Part 2).
Subject completion	A subject who has completed all phases of the study including the last scheduled procedure as shown in the Schedule of Visits and Procedures.
“Should” vs “Must”	Use of the word “should” means that it is suggested or recommended, but not required, whereas the use of the word “must” means that it is required.
Concurrent Medication	A medication that the study subject is taking at the time of enrollment or after
Concurrent Treatment	A procedure or other non-medication medical treatment that the study subject is receiving at the time of enrollment or after.
eg,	for example
ie,	in other words
Prior Medication	A medication taken by the study subject within time period specified in entry criteria prior to enrolling in the study. Other prior medications within 3 months prior to enrolling into the study.
Prior Treatment	A procedure or other non-medication medical treatment received by the study subject within time period specified in entry criteria prior to enrolling in the study. Other prior treatments within 3 months prior to enrolling into the study.
Study eye	The designated eye for use in analysis of IOP effects will be based on the eye with the higher IOP at Day -1, Hour 0. If both eyes qualify, the eye with the higher IOP at Baseline (Day -1) Hour 0 will be the study eye. If both eyes have the same IOP value at this timepoint, the right eye will be the study eye.

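### In Part 2 the early-exit minimum ends at the Day 14/Exit Hour 0 procedures, so a subject who stops early can leave within protocol with no post-dose ECG, visual field or fundus exam

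*Protocol*

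**What the plan says.** **Early stop of treatment (Protocol 8.8, Part 2).** "the Day 14/Exit (Hour 0) procedures, at a minimum should be performed".

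**Early exit from the study (Protocol 8.9.1).** The section first refers the site onward: "See Schedule of Visits and Procedures for specific data to be collected at the time of study discontinuation". It then names, for subjects discontinued early, "the Day 14/Exit visit (Hour 0 timepoint at a minimum) for Part 2 should be performed at the last visit attended". Neither section treats a stop for an adverse event differently from any other stop.

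**What Hour 0 contains (Protocol 8.4.2, Days 4 and 14/Exit).** Adverse-event questioning, concomitant medication review, supine and standing blood pressure and heart rate, redness grading, visual acuity, slit lamp and IOP, followed by dosing and drug collection. Two items are blacked out.

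**Where the other tests sit (Table 3 and 8.4.2).**
- ECG: "Electrocardiogram (Day 14/Exit only", listed in the text under Hour 2.
- Visual field: Day 14/Exit only, from Hour 2 until the pupil is dilated.
- Fundus: "Fundus exam (including cup/disc ratio, post-pupil dilation) (Day 14/Exit, Hour 8 only".
- Laboratory and urine pregnancy tests: a separate heading, "Day 14/Exit only, once final dose has been administered".

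**Force of the wording (Table 8).** The word *should*, used in both 8.8 and 8.9.1, "means that it is suggested or recommended, but not required".

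**The concern.** This is the first study of the compound in humans (Protocol 1.4), and acceptable safety and tolerability is a stated hypothesis for both parts. SAP 5.4 names ECG, visual fields and dilated fundus examination among the safety assessments. In Part 2 each is scheduled once after dosing, at the end of treatment.

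A subject who stops early because of a cardiac, systemic or ocular event is one whose end-of-treatment result would be of particular interest. If the minimum for that subject leaves these tests out, the post-dose listings lean towards subjects who tolerated the drug, and an arm with more early exits loses more of its data. Exited subjects may also be replaced (3.3.2, 8.9.1), so an arm can reach its planned number of completers while the subjects who left have no post-dose entry for these tests.

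**Working it through.** No power, alpha or sample-size figure is in question, so the check sets the sections side by side.

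**Step 1. Trace each Day 14/Exit-only safety test.** Inputs: Protocol Tables 1 and 3 and section 8.4.2.

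| Test | Before dosing | After dosing, Part 2 | In the Hour 0 list? |
|---|---|---|---|
| ECG | Baseline | Day 14/Exit, Hour 2 | No |
| Visual field | Screening, Baseline | Day 14/Exit, from Hour 2 | No |
| Fundus exam | Screening | Day 14/Exit, Hour 8 | No |
| Laboratory tests | Screening | Day 14/Exit, after final dose | Listed separately; unclear at early exit |
| Urine pregnancy test (where applicable) | Baseline | Day 14/Exit, after final dose | Listed separately; unclear at early exit |

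**Step 2. Could the blacked-out Hour 0 items be one of these?** No. All five tests appear as visible, separately named rows in Table 3, so the redacted rows are other procedures.

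**Step 3. Does an earlier visit supply a post-dose value?** No. The Part 2 Day 1 list contains none of the five, and the Day 14/Exit-only labels exclude Day 4.

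**Step 4. Compare with the minimum.** A site that does exactly what 8.8 and 8.9.1 set as the minimum collects 0 of the 3 tests placed at Hour 2 or later. For the other 2 the text supports two readings. They stand outside the Hour 0 list, which suggests they are not part of the minimum. But their trigger is the final dose, and a subject who has stopped treatment has already had it, which suggests they are due. For a completer the trigger is plain, because the Hour 0 list ends with "Site to administer study medication at end of Hour 0 examination". For an early stopper it is not. Column positions in Table 3 cannot settle this, because the table was read from PDF.

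**Step 5. Does the cross-reference close the gap?** Section 8.9.1 points to the schedule for what to collect at discontinuation, but Table 3 has no early-exit column.

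**Step 6. Size.**
- Per subject: 3 of the 5 tests can be absent on any reading, and 2 more on one reading.
- Per arm, with about 24 subjects per AGN-227535 group and 12 on timolol: one exit at the minimum removes 1/24 = 4.2% or 1/12 = 8.3% of the arm's subjects from the post-dose listings of these tests.
- Number of exits: not given. The synopsis counts do not agree on it. About 95 assigned against 18 + 60 = 78 completing implies 95 − 78 = 17 non-completers across both parts. But 24 + 24 + 12 = 60 treated in Part 2 against 60 completing implies none there.

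**The case against.** **Hour 0 is a floor, not the rule.** Section 8.9.1 names the Day 14/Exit visit and mentions Hour 0 only as the least acceptable. This stands: the gap is permitted, not prescribed. But a floor defines what counts as compliance, and leaving out all three tests would not be a deviation. Because of the Table 8 definition, even the floor is only a recommendation.

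**The investigator can order more.** Section 8.5 allows extra examinations, 8.7 asks for follow-up of ongoing adverse events, 8.7.4 requires follow-up of serious ones, and 8.9.1 covers events within 14 days after the last dose. These are real safeguards for the individual. None names an ECG, visual field or fundus exam for early exits, so collection may differ between sites.

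Four stronger readings are tempting, and the documents do not support them.

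- *That all five tests are certainly missed.* Only three are firm. The laboratory and pregnancy tests can be read as already due.
- *That a departing subject goes unchecked.* The Hour 0 minimum includes adverse-event questioning, postural blood pressure and heart rate, visual acuity, slit lamp and IOP.
- *That Part 1 shows a fuller exit standard.* Its Day 2/Exit visit is itself a single Hour 0 visit. It includes a fundus exam and pregnancy test but no ECG, laboratory test or visual field.
- *That a reported abnormality rate would be biased.* SAP 10, 10.1.2 and 10.1.6 present these data as listings only, so no rate, bound or test is planned. Part 2 subjects who stop for an adverse event still count in the adverse-event tables (SAP 10.1.1).

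**Conclusion.** The concern holds for the ECG, visual field and fundus exam: as written, a Part 2 subject can stop early for any reason, including an adverse event, and leave within protocol with no post-dose value for any of them. For the laboratory and pregnancy tests the finding is an ambiguity, not an established omission.

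The consequence is missing rows in the safety listings, related to tolerability, in a first-in-human study. It is not a biased formal test. How many subjects are affected cannot be derived from the documents. The conclusion rests on the text alone and needs no assumed dropout rate. It does assume that some sites would collect no more than the stated minimum.

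**What to change.** 1. Reconcile sections 8.8 and 8.9.1 with Table 3 so that the Part 2 early-exit minimum covers the safety assessments already scheduled only at Day 14/Exit: ECG, visual field and fundus exam, and explicitly the laboratory tests and, where applicable, the urine pregnancy test. Make this subject to the subject's agreement.
2. Add an Early Exit column to Table 3, so that the cross-reference in 8.9.1 leads to an actual list.
3. Choose between *should* and *must* deliberately, given how Table 8 defines them.
4. State in SAP 10 that values collected at early exit are listed as end-of-treatment values.

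**Cost.** An amendment to two paragraphs and one table, a sentence in the SAP, and a longer exit visit for the few subjects who leave early. The tests are those completers already have, so no new procedure or equipment is needed.

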## **8.9. Early Study Exit Procedures**

### **8.9.1. Subject Discontinuation/Withdrawal from the Study**

- A subject may withdraw from the study at any time at his/her own request, or may be withdrawn at any time at the discretion of the investigator for safety, behavioral, compliance, or administrative reasons;
- If the subject withdraws consent for disclosure of future information, the sponsor may retain and continue to use any data collected before such a withdrawal of consent;
- If a subject withdraws from the study, he/she may request destruction of any samples taken and not tested, and the investigator must document this in the site study records;
- A subject who is enrolled, but who had significant deviation from protocol-specified inclusion/exclusion criteria, may be discontinued from participation in the study;

- If a female becomes pregnant during the study, the investigator will notify Whitecap Biosciences immediately after the pregnancy is confirmed and the subject will stop taking study treatment. The subject will be discontinued from the study after appropriate safety follow-up. See Section 6.4.3 for Procedures for Pregnancy Follow-up and Reporting;
- Subjects who are exited before completing the study may be replaced.

See Schedule of Visits and Procedures for specific data to be collected at the time of study discontinuation and follow-up and for any further evaluations that need to be completed. If a subject is discontinued prior to completing the study, the procedures outlined for the Day 2/Exit visit (for Part 1) or the Day 14/Exit visit (Hour 0 timepoint at a minimum) for Part 2 should be performed at the last visit attended.

When a subject exits before completing the study, the reason for the early exit will be clearly documented on the appropriate eCRF.

If the subject exits before completing the study, any serious adverse events or treatment-related non-serious adverse events occurring within 14 days after the last dose of study treatment should be reported to the Site.

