**Part 1 - Day 2 (Hour 0)**

- Adverse event (AE) query

- Concomitant medications and treatments
- Postural (supine/standing) blood pressure and heart rate
- Urine pregnancy test (females of child-bearing potential only)
- Macroscopic (gross) hyperemia evaluation
- Visual acuity (VA): Manifest refraction performed at Baseline (Day -1) should be used for visual acuity evaluation. Manifest refraction(s) may be repeated, if in the opinion of the investigator, it is necessary.
- Slit-lamp biomicroscopy
- IOP (GAT)
- Fundus exam (including cup/disc ratio, post-pupil dilation)

Following the completion of the Day 2/Exit examination, the subject will exit the study.

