- On proper dosing of ocular medications and to dose study medication as directed: administer one drop in each eye each evening (between 1900 and 2100 hours) starting the evening of Day 1 and each morning (between 0700 and 0900 hours) through the evening of Day 13. The final dose of study medication on the morning of Day 14/Exit will be administered by site personnel after the Hour 0 examination. Subjects will be reminded to take their study medications approximately 12 hours before their Hour 0 appointments the evening prior to a post-baseline study visit and to not dose in the morning of Days 4 and 14. If desired, subjects will also be given the option for periodic (eg, daily) reminders from the Site to take their study medications each morning and evening;
- On proper storage conditions for study medications. The study medications should be kept in their unit carton (box). Do not show the bottles to other subjects or study staff (except the individual who dispenses the study medication to the subject). The study medications may be stored at room temperature during the study period (between 59°F and 77°F);
- To bring all used and unused study medication to all visits and to remind subjects that all study medications will be collected by the site at the Day 14/Exit visit.

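### In the readable text, protocol 8.9.1 states a 14-day post-dose reporting window only for early exits; separately, SAP 10.1.1 tabulates serious AEs where protocol 9.3.2 specifies serious TEAEs

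*Protocol*

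**What the plan says.** **Collection after the last dose.** Protocol Section 8.9.1 opens the relevant sentence with a condition, "If the subject exits before completing the study", and then recommends that "any serious adverse events or treatment-related non-serious adverse events occurring within 14 days after the last dose of study treatment" be reported to the site. The verb is *should*, which Table 8 defines as a recommendation rather than a requirement.

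For everyone, Section 8.7 has investigators identify and report events "throughout the study (from subject signing of informed consent through study exit". Events marked as ongoing at exit are followed until they resolve or are judged chronic or stable. Section 8.7.4 adds: "Any serious adverse event must be immediately reported but no later than 24 hours after learning of the serious adverse event". The readable text gives that duty no end date, and the section closes with a redacted reference to further detail.

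**Timing of exit.** In Part 2: "The final dose of study medication on the morning of Day 14/Exit will be administered by site personnel after the Hour 0 examination". The last assessments that day are at Hour 8, and then: "Following the completion of the Day 14/Exit examination, the subject will exit the study". In Part 1 the single dose is given on Day 1 after the Hour 0 assessments. Day 2 has an Hour 0 visit only, and then: "Following the completion of the Day 2/Exit examination, the subject will exit the study".

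**Tabulation.** Protocol Section 9.3.2 and the synopsis call for rows of serious TEAEs and treatment-related serious TEAEs, and Section 9.3.2 leaves the TEAE definition to the SAP. SAP Section 10.1.1 tabulates serious AEs and treatment-related serious AEs for Part 2. It defines treatment-emergent by onset in the treatment period, or worsening after first dose, and does not say when that period ends. SAP Section 1.1 lists three changes from the protocol, none about adverse events.

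**The concern.** This is the first study of the drug in humans, and safety comes first in its objective. The sponsor judged a 14-day look-back after the last dose worthwhile for subjects who leave early. Part 2 completers receive the full course, yet the readable text gives no reason for a shorter window for them.

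The type of event most exposed is a late, treatment-related, non-serious one. Such an event can matter for decisions. The review trigger in Section 3.3.1 is two or more severe events of the same kind that are possibly drug-related, and it does not require seriousness. Section 3.4 bases dose escalation and Part 2 dose selection on all available Part 1 data.

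The SAP wording raises a smaller, separate question: which events belong in the serious rows. As written, a serious event before the first dose could be counted against the arm to which the subject was later assigned. It is also unclear how a late event in an early exit would be classified.

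**Working it through.** The plan gives no figure on this point to reproduce. There are two checks.

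**1. How much of the 14-day window falls before exit for a completer**

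Inputs: the window from Section 8.9.1; dose and exit times from Sections 8.4.1, 8.4.2 and 8.6.

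- Window: 14 × 24 = 336 hours.
- Part 2 completer: dosed after Hour 0, exits after Hour 8, so about 8 hours. 8/336 = 2.4%. Remaining: 336 − 8 = 328 hours, or 328/24 = 13.7 days.
- Part 1 completer: dosed after Day 1 Hour 0, exits at Day 2 Hour 0, so about 24 hours. 24/336 = 7.1%. Remaining: 336 − 24 = 312 hours, or 312/24 = 13.0 days.

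These figures describe the schedule and assume no event rate. What the readable text provides after exit is as follows:

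| Event | Early exit | Completer |
|---|---|---|
| Ongoing at exit | Followed (8.7) | Followed (8.7) |
| New, serious | 14-day report recommended (8.9.1); site must report once aware (8.7.4) | Site must report once aware (8.7.4); no stated window or prompt |
| New, non-serious, treatment-related | 14-day report recommended (8.9.1) | No stated window or prompt; injury contact from consent (10.2.3) |
| New, non-serious, unrelated | Not requested | Not requested |

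The two groups differ only in the second and third rows, and the third has no site duty behind it. The only post-exit instruction in Section 8.6 concerns pregnancy, for 30 days. The general reminder there to contact the site covers difficulties during participation.

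**2. Which events the SAP wording could add to the serious rows**

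| Row (Part 2) | Protocol 9.3.2 | SAP 10.1.1 |
|---|---|---|
| Serious | TEAEs only | All AEs |
| Treatment-related serious | TEAEs only | All AEs |

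The rows differ by serious events that are not treatment-emergent. There are two kinds.

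- *Before first dose.* Collection starts at consent and screening can begin at Day −50. If a condition found before dosing is not judged pre-existing, Section 8.7.1 says "the condition should be reported as a pre-treatment adverse event". The Safety population is treated subjects, so only those later dosed contribute. A pre-dose event can hardly be drug-related, so the related-serious row should barely move.
- *After the treatment period.* Its end is not stated. SAP Section 7.2 counts exposure from first to last dose inclusive. If the treatment period is read the same way, an early exit's event 10 days after the last dose is not treatment-emergent. If it is read to the end of collection, the event is. The SAP's reference to events reported during the study does not settle this.

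**The case against.** The strongest reply is that completers are not left without cover. Sites must report any serious event they learn of, events ongoing at exit are followed, and the consent content in Section 10.2.3 tells every subject whom to contact about study-related injury. The 8.9.1 sentence is itself only a recommendation, does not appear among the subject instructions in Section 8.6, and concerns people who may leave for safety reasons and miss visits. A longer window for them could be deliberate. The redacted reference in Section 8.7.4, redactions in the rationale for duration of observation, and the removed consent pages may also hold more. All of this stands and limits the point to what the readable text shows. None of it states a 14-day window for completers.

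On the SAP, the reply is that serious AEs include serious TEAEs, so the broader row errs towards disclosure, and that serious events are listed for both parts. That also stands. It limits the effect but does not reconcile the two documents.

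Three stronger readings are tempting and not supported:

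- *That serious events in completers go unreported.* Section 8.7.4 has no stated end date, so a serious event the site hears of must still be reported.
- *That the SAP conceals serious events.* The listings in SAP Section 10.1.1 rule this out.
- *That the uncovered days can be multiplied by planned completers to size the loss.* Of the 60 planned in Part 2, 12 receive timolol. Exclusion criterion 27 bars only earlier Part 2 randomization, so a Part 1 subject may also be in Part 2. The product would in any case say nothing about events missed.

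**Conclusion.** The point holds as a minor one, with two separate parts.

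First, in the readable text a 14-day post-dose reporting window is stated only for early exits. New-event collection for completers stops about 8 hours (Part 2) or 24 hours (Part 1) after the last dose. What is missing is a stated window and a prompt, mainly for late treatment-related non-serious events.

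Second, the serious rows in SAP Section 10.1.1 depart from protocol Section 9.3.2 without being declared, and the end of the treatment period is open. The expected effect on counts is small.

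The documents give no late-event or early-exit rate, so no number of missed or misplaced events is claimed. No effect on a dose decision has been shown, and the IOP analysis is unaffected. The first part assumes that the redacted and removed text contains no equivalent instruction for completers.

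**What to change.** 1. **Protocol.** In Sections 8.6, 8.7 and 8.9.1, instruct every treated subject in both parts to report to the site any serious or treatment-related non-serious event within 14 days after the last dose, whether they complete or leave early. In Section 8.6 this can sit beside the pregnancy instruction.
2. **SAP Section 10.1.1, serious rows.** Restrict the serious and related-serious rows to TEAEs, as in protocol Section 9.3.2, and list pre-treatment serious events separately. This correction stands even if the protocol is not amended.
3. **SAP Section 10.1.1, TEAE window.** If step 1 is adopted, run the window from first dose through 14 days after the last dose for every subject, with a footnote that unrelated non-serious events are captured only to exit. If it is not adopted, end the window at exit for all subjects and list later events separately.

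The cost is about one sentence in each of three protocol sections and one SAP definition, with no added visit or call. There would be slightly more event reporting and a wait of up to 14 days after the last subject's last dose before the single database lock. Reporting would still depend on subjects coming forward, and the all-TEAE row would mix two collection windows, which is why it needs the footnote.
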